At our institution we examined data from the initial cohort of 19 COVID-19 patients to use CGM in OSUWMC MICU. Among these patients, 89% were on ventilators, 37% on vasopressors, and 42% on hemodialysis at the time of sensor placement.¹¹ Despite the severity of critical illness, MARD was 13.9% with no apparent association with oxygen saturation, mean arterial pressure, vasopressor use, renal replacement, anticoagulation, or ventilator support. Time in range (70-180 mg/dl) on day 1 was 64+/- 23%, and on days 2-7 was 72+/-16%. Time below range (<70 mg/dl) was 1.5+/-4.1% on day 1 and 0.16+/-0.35% on days 2-7¹¹. We have since expanded our analysis to include a larger cohort of the first 50 COVID-19 patients on CGM. Of these patients, 92% were on ventilators, 46% on vasopressors, 33% on hemodialysis, and 74% were on steroids at the time of sensor placement. In our larger cohort, the aforementioned factors were again not associated with sensor accuracy. Hybrid protocols of POC glucose checks with CGM use have been used in other small studies of extremely critically ill ICU patients with COVID-19 (n=61 subjects total in four studies)^{5-7,10}. One study did find decreased accuracy with cardiac arrest.⁵ Across these studies, MARD ranged between 11.1-13.9% for Dexcom G6^{6,10,11} and Clarke error grid analysis showed 98-98.2% in zones A+B.^{6,10} In a recent larger study conducted among 218 hospitalized non-ICU patients, mild to moderate anemia was not shown to impact sensor accuracy, however more severe anemia (hemoglobin <7g/dL) was found to correlate with higher ARD (17.8%).¹² This same study demonstrated no association between hyperglycemia and sensor accuracy but did demonstrate a slight increase in MARD (18.8%) and ARD (14.5%) with glucose <70mg/dl.¹² In a study by Boom et al. focused on hypoglycemia reduction, 177 medical ICU patients were randomized to CGM or standard of care. In this study, hypoglycemia and was reduced from 12 times per day to fewer than 1 time per day and overall glucose control was similar between groups.¹³ Other ICU studies have also showed acceptable accuracy in ICU patients, despite the use of older technologies.^{14,15} Moreover, there is evidence that accuracy can be offset by increased frequency of monitoring, as is the case with CGM.¹⁶ While there is some concern surrounding the effects of edema or changes in fluid volume on sensor accuracy, a study among congestive heart failure patients demonstrated no association between MARD and BNP or changes in plasma volume, this despite the use of older less accurate technology.¹⁷

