
Diabetes is a worsening epidemic worldwide. In the United States, the prevalence has quadrupled between 1980 and 2020 with an estimated 21.9 million adults living with diabetes¹⁸. Hospitalizations among patients with diabetes account for 30% of the total medical cost of inpatient care with more than 7.8 million hospital discharges in 2017 in the United States¹⁹. Hypoglycemia, hyperglycemia, and glycemic variability in the hospital are associated with poor health outcomes including infection, acute renal failure, and death²⁰⁻²⁴. Traditional POC capillary glucose monitoring measures glucose at one point in time and often misses hypoglycemia^{23,25,26}, especially overnight or asymptomatic episodes, whereas continuous glucose monitoring (CGM) can help provide details of glucose continuously as well as velocity and direction of change over time. The ability to visualize

glucose trends or direction and velocity of glucose offers tremendous additional benefit over traditional discrete POC glucose monitoring.

Additionally, CGM can improve efficiencies in the critical care environment and reduce nursing care burden.^{2,13} According to the Bureau of Labor Statistics the United States is facing an unprecedented nursing shortage which is expected to worsen over the upcoming decade. Intensive inpatient POC glucose monitoring is an arduous, time-consuming task, often resulting in insufficient frequency of testing and testing that is mistimed with oral intake or insulin administration.²⁷ The use of inpatient CGM holds tremendous promise to improve patient outcomes, reduce nursing workload, and associated healthcare costs, however, the inpatient implementation of CGM beyond the pandemic presents unique implementation challenges and warrants further inquiry.

Description of Technology.

The Dexcom G6 CGM (Dexcom Inc) measures interstitial fluid glucose. The G6 system consists of 3 key parts: the sensor wire, a transmitter, and a display device. In addition, a CGM Dashboard will be used to display data at the nurse's stations.

The sensor comprises a water-resistant sensor pod that is worn on the skin, and the sensor wire that is inserted just under the skin (depth is less than 0.5 inches) using the single-use applicator. The sensor can be worn for 10 days and continuously measures glucose levels. In this study the sensor will be worn on the back of the arm.

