Sustained use	
Revert from Q4 hour to Q1 hour POC testing if:
 
 1) CGM >20% difference from the POC when the glucose is >100 mg/dl 2) CGM >20 mg/dl difference from the POC when the glucose is <100 mg/dl 3) Revert back to Q4 hour POC testing when two consecutive sensor-meter pairs approximately 1-hour apart meet the initial validation criteria 
Revert from Q4 hour to Q2 hour POC testing for a duration of 6 hours for one of the following clinical status events occurring in isolation:
 
 4) Intubation 5) Pressor support initiated (Levophed dose <0.5 mcg/kg/min or equivalent) 6) New cardiovascular event (MI, CVA) 7) Initiation or discontinuation of nutrition support (i.e., enteral feed, total parenteral nutrition) 8) Hemoglobin <7g/dL 9) CGM or POC glucose <70mg/dl (follow OSUWMC hypoglycemia policy for initial treatment and monitoring) 10) Predicted low alert (glucose predicted to be <55mg/dl in the following 20 minutes) 11) Acidosis with pH <7.3 12) Signs and symptoms do not match glucose readings, particularly for hypoglycemia 
Revert from Q4 hour to Q1 hour POC testing for a duration of 6 hours for two or more of the above clinical status events occurring together (example: patient is intubated and starts pressor support)
 
If after 6 hours no additional clinical scenarios featured above have developed than Q4 hour POC testing can resume after initial validation using two consecutive sensor-meter pairs.
 
Obtain 1 time POC glucose if:
 
 13) No glucose value appears on android screen (due to signal loss, Low/High measure) 14) Low threshold alert (<100mg/dl)
Stop CGM use	
Stop use of CGM for insulin titration or glucose monitoring and revert from Q4 hour to Q1 hour POC testing (do not remove CGM sensor until sensor expires) for the following conditions:
 
 1) Refractory shock (Levophed dose >0.5 mcg/kg/min or equivalent) 2) Cardiac arrest 3) Newly developed diabetic ketoacidosis (DKA) (pH <7.3 or serum bicarbonate <15 mEq/L in the setting of elevated ketones) 4) Newly developed hyperosmolar non-ketoacidosis (HONK) 5) Pitting edema, anasarca, blue or purple discoloration to bilateral upper extremity 6) Initiation of treatment with high dose acetaminophen (>1 gram Q6 hours) 
Initiation of treatment with hydroxyurea

III. Procedures

A. Research Design

Hybrid Research Design

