The study will take place at OSUWMC. At OSUWMC there are approximately 13,000 hospitalizations with a diagnosis code for diabetes each year and current annual inpatient diabetes consult service and diabetes educator consults are roughly 3000 per year. OSUWMC has implemented a comprehensive, hospital-wide inpatient diabetes program since 2006, including streamlined computerized diabetes related order sets, carbohydrate-based insulin dosing, education, and ongoing review of outcomes. OSUWMC converted to EPIC EHR in 2011 for both inpatient and outpatient electronic medical records. The medical centers MICU has been utilizing Dexcom G6 CGM for COVID-19 patients since May of 2020 and to date has utilized CGM in over 132 critically ill COVID-19 patients. The study will take place in the MICU. The MICU is a 48-bed critical care center and employs 152 staff nurses. Patients will be identified through daily screening of patients and associated glycemic control in the MICU to identify potential participants with hyperglycemia (glucose >250mg/dl) or those currently on IV insulin. In 2019, prior to the COVID-19 pandemic, OSUWMC had 1,065 unique patient admissions in which the patient had a glucose >250mg/dl over the course of their MICU stay. Within the MICU patient population, patients with more severe illness and those with conditions that may interfere with CGM sensor accuracy will be excluded from participation. Full inclusion and exclusion criteria are as follows:

Eligible individuals are:

- 1) adults >18 years old,
- 2) admitted to OSUWMC MICU and

- 3) have hyperglycemia (glucose >250mg/dl) or are currently on IV insulin.

Non-eligible individuals are:

- 7) Current COVID-19 infection,
- 8) Refractory shock (Levophed dose >0.5 mcg/kg/min or equivalent)
- 9) Actively being treated for diabetic ketoacidosis (DKA)
- 10) Actively being treated for hyperosmolar non-ketoacidosis (HONK)
- 11) Pitting edema, anasarca, blue or purple discoloration to left upper extremity
- 12) Treated with high dose acetaminophen (>1 gram Q6 hours)
- 13) Treated with hydroxyurea
- 14) Are pregnant, patients
- 15) Using home insulin pump therapy during hospitalization, or
- 16) Reside in a corrections institution.

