- No more than 1 episode of inappropriate insulin dose resulting in severe hypoglycemia (glucose <55mg/dl) after initial sensor validation
- No more than 1 episodes of iatrogenic DKA (pH <7.3 or serum bicarbonate <15 mEq/L in the setting of elevated ketones) or hyperosmolar nonketotic state (osmolality \geq 320mOsm/kg with BG >600mg/dl and pH >7.3 or serum bicarbonate >15 mEq/L)
- No episodes of severe adverse events resulting in prolonged hospitalization, or other life-threatening complication that attributed to the study intervention
- No severe adverse events resulting in death, or other life-threatening complication that is attributed to the study intervention
- No severe adverse event resulting in prolonged hospitalization, or other life-threatening complication that attributed to the study intervention and is expected to recur

Oversight and monitoring. Study team oversight of nursing use of the CGM system will be performed through a combination of (1) daily evaluation of EHR and CGM Clarity data and (2) through rounding on CGM patients (mon-Friday by PI ([name]), Co-I ([name]) and/or study coordinator (to be named) (Saturday, Sunday and holidays by the MICU charge nurse who will communicate that day with study team members. Daily rounds will allow the study team to continuously evaluate protocol fidelity and identify any safety concerns. The study staff will evaluate CGM use daily through Clarity CGM and EHR data to determine the following:

3. Was initial validation criteria achieved correctly and at what frequency
4. Is ongoing validations performed Q4 hours and according to validation criteria
5. If validation is met did the nurse begin hybrid use with non-adjunctive CGM use
6. Using clarity reports study staff will assess the presence of alarms (e.g., <100mg/dl, >300mg/dl, predictive hypoglycemia) Alarms will be reviewed daily by research staff to ensure hypoglycemia and hyperglycemia are being treated in accordance with OSUWMC guidelines.
7. Those patterns of hyperglycemia or hypoglycemia assessed every 24 hours, will be reported to primary team via pager/direct message to allow changes to insulin dosing as needed (e.g., max drip rate for IV insulin titration).
8. Assessment of change in clinical status criteria (Table 1) in which per protocol the nurse would increase frequency of POC testing and validation.

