9. Assessment of Stop CGM use criteria (Table 1) in which per protocol the nurse would no longer use the CGM for glucose monitoring or insulin titration.

RQ 1: Establish the clinical utility, fidelity, and adoption of Dexcom G6 CGM as a tool for making dosing decisions within a CGM+POC protocol among medical intensive care unit (MICU) patients.

Rationale/Approach. We will conduct a prospective cohort observational analysis among critically ill patients on IV insulin or those with hyperglycemia (>250mg/dl) in OSUWMC MICU. The research will allow us to examine the clinical utility and implementation of CGM as the standard of care in a critical care environment. We hypothesize that the majority of insulin dosing decisions will be made using non-adjunctive CGM and CGM, with the availability of trend and alarm data, will alter nursing dosing decisions from standard guidelines.

Procedures. Once consent is obtained, the MICU staff nurse will insert the Dexcom G6 sensor, set up the system, pair the transmitter on patients, and connect patient data to a centralized nurse's station CGM Dashboard in the MICU (N=100). The CGM + POC protocol will be used to validate at which time the CGM will be used for non-adjunctive insulin dosing decisions. POC testing will be performed Q4 hours for continued validation of the CGM with more frequent sustained POC validation during periods of rapid clinical change (Table 1).

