An investigator shall submit to the sponsor and to the reviewing IRB a report of any unanticipated adverse device effect occurring during an investigation as soon as possible, but in no event later than 10 working days after the investigator first learns of the effect (21 CFR 812.150(a)(1)). A sponsor who conducts an evaluation of an unanticipated adverse device effect under 812.46(b) shall report the results of such evaluation to the FDA and to all reviewing IRB's and participating investigators within 10 working days after the sponsor first receives notice of the effect. Thereafter the sponsor shall submit such additional reports concerning the effect as FDA requests (21 CFR 812.150(b)(1)).

E. Study and individual participant stopping criteria:

We plan to enroll participants in waves of 20 with ongoing analysis between waves. We plan to stop the study for the following conditions in consultation with the data safety monitoring board assigned to oversee safety activities and the study:

- Failure to meet initial validation criteria within 24 hours in 20% of participants
- CGM-meter pairs obtained during routine monitoring following initial validation without a change in clinical status prompting hourly monitoring meeting the following criteria:
 - Failure to detect clinically significant hypoglycemia (≥ 2 episodes): CGM value >100 mg/dl with no Urgent Low Soon alert while POC BG <70 mg/dl
 - Failure to detect severe hyperglycemia (≥ 2 episodes): CGM value <180 mg/dl when POC BG >400 mg/dl
 - Inappropriate treatment (≥ 2 episodes): CGM value triggers the opposite action than the POC BG value (CGM >180 mg/dl while POC BG <70 mg/dl or vice versa).
- ≥ 2 episodes of inappropriate insulin dose resulting in clinically significant hypoglycemia (glucose <55 mg/dl) after initial sensor validation
- ≥ 2 episodes of iatrogenic DKA (pH <7.3 or serum bicarbonate <15 mEq/L in the setting of elevated ketones) or hyperosmolar nonketotic state (osmolality ≥ 320 mOsm/kg with BG >600 mg/dl and pH >7.3 or serum bicarbonate >15 mEq/L)
- ≥ 2 episodes severe adverse events resulting in prolonged hospitalization, or other life-threatening complication that are attributed to the study intervention
- Any severe adverse event resulting in death, or other life-threatening complication that is attributed to the study intervention

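### The CGM stop rule puts the arm signs on both arms, the matching exclusion puts them on the left arm, and the sensor arm is never named, so signs confined to the sensor arm may not stop CGM dosing

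*Combined protocol and SAP*

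**What the plan says.** Three places in the combined protocol and SAP bear on this point.

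- **Stop rule** (II, CGM + POC Protocol, Table 1, Stop CGM use, item 5): "Pitting edema, anasarca, blue or purple discoloration to bilateral upper extremity". When it is met, CGM is no longer used for titration or monitoring, POC testing goes to hourly, and the sensor stays in place until it expires.
- **Exclusion** (III.B Sample, non-eligible item 11): "Pitting edema, anasarca, blue or purple discoloration to left upper extremity". The paragraph above the list explains that, besides the more severely ill, "those with conditions that may interfere with CGM sensor accuracy will be excluded from participation".
- **Placement** (II, Description of Technology): "In this study the sensor will be worn on the back of the arm". No side is given here or elsewhere.

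The daily oversight list (III.C, item 9) checks the same table: "Assessment of Stop CGM use criteria (Table 1) in which per protocol the nurse would no longer use the CGM". Nurse training in III.C also covers the stop criteria.

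**The concern.** The two items list the same signs in almost the same words and differ only in the arm. Neither is tied to the arm that carries the sensor, which is the arm that matters if the purpose is to protect sensor accuracy. A bedside nurse who takes *bilateral* in its ordinary sense would keep dosing insulin from the CGM when only the sensor arm is discolored.

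The pair is also inconsistent over time. On that reading, left-arm discoloration keeps a patient out of the study, but the same sign appearing on day 3 would not stop CGM use.

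At stake is whether a stated safety rule acts where it is needed. The daily check and the training do not settle the matter, because both rely on the same Table 1 criteria.

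**Working it through.** The plan gives no figure to reproduce. The check compares the wording and counts cases.

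**Step 1. Signs that can be local to one arm.** Item 5 lists three signs. Anasarca is generalized, so the arm phrase matters little for it. That leaves two signs: pitting edema and discoloration.

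**Step 2. The stop rule, for a sign confined to the sensor arm.** The text allows three readings.

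| Reading of the stop item | Pitting edema | Discoloration | Missed |
|---|---|---|---|
| Both arms; phrase governs the whole list | no stop | no stop | 2 of 2 |
| Both arms; phrase governs discoloration only | stop | no stop | 1 of 2 |
| Either arm | stop | stop | 0 of 2 |

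**Step 3. Discoloration by location and sensor arm.** Three locations (left only, right only, both) times two sensor arms gives 3 × 2 = 6 combinations. The sensor arm is affected in 4 of them: left sign with left sensor, right sign with right sensor, and both arms with either sensor.

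- Stop rule, both-arms reading: fires in 2 of 6, and misses 2 of the 4 in which the sensor arm is affected.
- Stop rule, either-arm reading: fires in 6 of 6, including the 2 in which only the other arm is affected.
- Exclusion as written: fires in 4 of 6 (left only or both). It misses right-only discoloration with a right-arm sensor, and it excludes left-only discoloration even when the right arm would carry the sensor.
- Wording tied to the sensor arm: fires in exactly the 4 that involve the sensor arm.

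**Step 4. The exclusion, for a sign confined to the intended sensor arm.** With left-arm placement it misses 0 of 2 on any reading. With right-arm placement it misses 2 of 2 if the phrase governs the whole list, or 1 of 2 if it governs discoloration only.

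**Step 5. What a missed stop changes.** Scheduled POC tests a day are 24/4 = 6 under Q4-hour testing and 24/1 = 24 under the stop rule, a difference of 24 − 6 = 18 per patient-day. The patient also stays on CGM dosing. This contrast applies only while the paired checks agree, because a discordant pair already brings hourly testing.

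**Step 6. What cannot be derived.** The documents give neither the frequency of one-sided signs, nor the placement side, nor any accuracy effect of local edema or discoloration. The number of patients affected is therefore unknown.

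**The case against.** **The word may have meant either arm.** The phrase is loosely built, with *bilateral* before a singular noun, and the authors may have meant signs on either side. On that reading nothing is missed. This stands, so a reader should not infer that the rule certainly fails for sensor-arm signs. The documents support only that the text is inconsistent and, on the ordinary meaning of the word, leaves a gap.

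**The exclusion probably reflects left-arm placement.** This is plausible, and with left-arm sensors the exclusion works. But no section says so, and on the both-arms reading the stop rule would still miss discoloration of the left arm alone. A reader might also infer that patients with sensor-arm signs pass both rules. That needs right-arm placement, which no section describes, together with the both-arms reading.

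**Other safeguards act at patient level.** This is largely right.

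- Table 1 keeps POC testing hourly until two consecutive sensor-meter pairs, about an hour apart, agree within 20% or 20 mg/dl. No sensor guides dosing before that.
- Paired checks then continue every 4 hours, and a discordant pair returns the patient to hourly testing. CGM dosing is arguably suspended too, since the Table 1 threshold is the criterion for stand-alone use.
- A mismatch between symptoms and readings brings Q2-hour testing, and a reading below 100 mg/dl prompts a POC check.
- Section IV.E ends participation after two sensors fail validation.
- Section III.C adds that "Daily rounds will allow the study team to continuously evaluate protocol fidelity and identify any safety concerns".

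These limit the harm but do not replace the stop. The accuracy checks respond after a discrepancy shows at a paired reading, and two agreeing pairs return the patient to Q4-hour testing. The stop rule acts on the sign itself and has no stated route back. Edema and discoloration are not among the events that raise testing frequency. The study-level rules in IV.E, such as "CGM value triggers the opposite action than the POC BG value", count discordant pairs and not arm signs.

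**Accuracy may not suffer.** The Background notes concern about edema but reports that "a study among congestive heart failure patients demonstrated no association between MARD and BNP or changes in plasma volume". That study looked at BNP and plasma volume, so it does not settle the effect of local arm signs. Equally, nothing in the documents shows that such signs degrade accuracy. The plan has nevertheless chosen these signs as stop and exclusion criteria, so they should work at the sensor site.

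**Conclusion.** The point holds as an inconsistency in a safety rule. The stop item and the exclusion name different arms, and the placement arm is unstated. The stop rule misses 2, 1 or 0 of the two local signs, depending on how *bilateral* and the reach of the location phrase are read. The entry-versus-later mismatch for left-arm discoloration arises on the both-arms reading.

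This is minor. No endpoint, sample size or analysis is affected, and validation, paired checks and rounds contain most of the risk. It is worth correcting because bedside staff apply the rule literally and the correction is nearly free.

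The conclusion rests on the current text alone. It assumes that no separate placement instruction exists outside the documents. A statement elsewhere that sensors always go on the left arm would settle the exclusion, but not the stop rule.

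**What to change.** 1. In Description of Technology, state which arm carries the sensor. The sensor is replaced every 10 days, after some imaging procedures and on failure, so say also whether a replacement may go on the other arm.
2. Reword Stop CGM use item 5 as: anasarca, or pitting edema or blue or purple discoloration of the upper extremity bearing the sensor.
3. Reword exclusion 11 in the same way, for the upper extremity intended for the sensor.
4. If pitting edema anywhere was meant to count, write *pitting edema at any site* in both items, so that neither rule is loosened.
5. Use the same wording in nurse training and in the daily stop-criteria check (III.C, item 9).

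Tying the rule to the sensor arm is preferable to naming either arm. The latter would stop CGM use for a sign confined to the other arm, for which the documents give no accuracy reason. If the sponsor did intend that, it should say so explicitly.

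**Cost.** Two list items, a short placement statement and one line of training. A few patients with sensor-arm signs would move from 6 to 24 scheduled POC tests a day (18 more per patient-day) and contribute less CGM-dosing time to RQ1. If the left arm is named for placement, the arm covered by the exclusion does not change. If the right arm is named, signs confined to the left arm would no longer exclude and signs in the right arm would.

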Sample Size Justification. The primary outcome for the power analysis is the percentage of time spent in target (70-180mg/dl). We estimate from previous studies^{13,28} that these values may have a standard deviation as high as 25 percentage points, in which case with 100 patients in each group we will have 80% power to detect a difference of 10 percentage points in time in range (e.g., 65 vs. 75); a moderate effect size of 0.4. If the standard deviation is lower (e.g., 15 as has been true in some studies), we will have greater power (99%) to detect a 10 point difference and are still well powered to detect smaller differences (e.g., 90% power for a 7 point difference). All power calculations assume an alpha of 0.05 and minimal statistical effects of clustering within the hospitals (e.g., unit or nurse level).

C. Detailed study procedures

Recruitment: Critical care clinical research coordinators will screen for preliminary eligibility and forward potential participant names to study team using a secure medical record in-basket process. The study team will determine eligibility. The study team will ask for permission for the patient to be approached. If permission is granted, the study team will verify eligibility and obtain informed consent from the patient or the patient's legally authorized representative. Consent will be obtained prior to research participation and CGM placement. Recruitment is expected at a rate of 5 patients per week over seven months. Our target recruitment will be 100 MICU patients.

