Procedures. Glucose data will be directly transferred from the MICU patients (N=100) to Android mobile phones/Dexcom G6 app which captures and stores glucose values every 5 minutes (up to 288 values/day for 100% CGM wear). CGM data is automatically transferred from phones/Dexcom G6 app to Dexcom Clarity. Individual patient discrete data will be downloads directly from the Clarity site. Historical controls meeting the gateway criteria (glucose >250 mg/dl or on IV insulin during admission) from the same MICU will be matched on the following factors: Diagnosis and type of diabetes, home insulin use, steroid use during hospitalization, vasopressor use, North vs. South MICU wings (NP team floor vs. resident team floor, respectively), and diabetic ketoacidosis (DKA)/hyperosmolar hyperglycemic syndrome (HHS) status. POC glucose values for historical controls (N=100) will be obtained directly from OSUWMC EHR. EHR data will be obtained through an information warehouse request providing time stamped, POC glucose value for each match patient. All data will be uploaded into STATA 15.0 where it will be cleaned and merged prior to analysis.

Variables and Measures. Demographic, admission, and diabetes specific variables of interest appear in Table 2 and will be collected from the EHR for MICU participants and for historical controls. Clinical condition variables will include presence of renal replacement, mechanical ventilation, ECMO, associated cardiac arrest or cerebrovascular accident and SOFA score. SOFA score was calculated, though noted to have limited discriminant function for predicting mortality.³² The SOFA score has been validated in critically ill patients³³, and is currently the scoring system recommended by the Sepsis 3 definition.³⁴ CGM and POC glucose data will be aggregated into glucose ranges and thresholds as described in Table 2.

Exploratory aim:

RQ 4: To assess hospitalization outcomes and conduct economic evaluation of the costs to deliver CGM implementation in the MICU.

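### RQ3 and RQ4 stop at 100 record-based historical controls without a stated reason; several matched controls per CGM patient would be a cheap gain in precision, although the present number is not an error

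*Combined protocol and SAP*

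**What the plan says.** The Sample Size Justification (III.B) bases power on percent time in 70-180 mg/dl. It assumes that "these values may have a standard deviation as high as 25 percentage points", which for a 10-point difference is "a moderate effect size of 0.4", and concludes that "with 100 patients in each group we will have 80% power to detect a difference of 10 percentage points in time in range". For an SD of 15 it adds that "we will have greater power (99%) to detect a 10 point difference" and cites "90% power for a 7 point difference".

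The control count is fixed in III.C. Under RQ 3 Procedures, "POC glucose values for historical controls (N=100) will be obtained directly from OSUWMC EHR", through an information warehouse request. RQ 4 Procedures again names 100 historical controls, with data from the EHR and billing. Controls must have had glucose above 250 mg/dl or been on IV insulin. They are matched on six factors: diabetes diagnosis and type, home insulin, steroids, vasopressors, MICU wing, and DKA/HHS status. No matching ratio is named (1:1 is inferred from the group sizes), and no control time window or matching algorithm is given.

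On supply, III.B says that in 2019 "OSUWMC had 1,065 unique patient admissions in which the patient had a glucose >250mg/dl over the course of their MICU stay". It also dates the current EHR from 2011.

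III.D describes a linear mixed model for CGM patients that is then repeated for controls, using control days with at least three POC values. It does not state a joint between-group model.

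**The concern.** The two sides of the comparison differ greatly in cost. Each CGM patient needs consent, a device, daily oversight and a place in a wave of 20. A control needs none of these. When one group is expensive and the other comes from existing records, taking several controls per patient is a standard way to gain precision, and the plan does not say why it takes only one.

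At stake is the precision of the RQ3 between-group contrast and, to a lesser degree, of the patient-level RQ4 outcomes. At SD 25 the planned 100 per group is one more than the 99 required for 80% power. The plan adds nothing for patients lost through failed sensors, hospice transition or withdrawal (IV.E), or for days dropped because CGM wear is below 70% (III.D).

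**Working it through.** **Inputs.** From III.B: 100 CGM patients, difference 10 points, SD 25 (upper case) or 15, alpha 0.05, minimal clustering. From III.D: two-sided tests. From III.B: 1,065 admissions in 2019. The CGM group is held at 100 and there are k controls per CGM patient.

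**Formulas.** SE = SD × sqrt(1/100 + 1/(100k)). Power = Φ(difference/SE − 1.96). The 95% CI half-width is 1.96 × SE. The difference detectable with 80% power is (1.960 + 0.842) × SE. Groups are treated as independent.

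**The plan's own figures (k = 1).**
- 10 points, SD 25: SE = 25 × sqrt(0.02) = 3.54; power 80.7% (80.4% by noncentral t). Stated 80%.
- 10 points, SD 15: 99.7%. Stated 99%.
- 7 points, SD 15: 91.0% (90.7% by t). Stated 90%.

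All three reproduce.

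**More controls, SD 25, every CGM patient receiving exactly k.**

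| Ratio | Controls | SE | Power, 10 points | CI half-width | Detectable difference | Power, 7 points |
|---|---|---|---|---|---|---|
| 1:1 | 100 | 3.54 | 80.7% | 6.9 | 9.9 | 50.8% |
| 1:2 | 200 | 3.06 | 90.4% | 6.0 | 8.6 | 62.8% |
| 1:3 | 300 | 2.89 | 93.4% | 5.7 | 8.1 | 67.9% |
| 1:4 | 400 | 2.80 | 94.7% | 5.5 | 7.8 | 70.7% |

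The SE falls by 13%, 18% and 21% at 1:2, 1:3 and 1:4. The limit with unlimited controls is 1 − sqrt(1/2) = 29%, so most of the gain is reached by 1:3 or 1:4.

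**Variable ratio.** If each matched set counts equally (control weight 1/k), the effective number of controls is 100/mean(1/k). Assume half the sets find one control and half find four. Then mean(1/k) = (1 + 0.25)/2 = 0.625 and the effective number is 160, although 50 × 1 + 50 × 4 = 250 controls are used. SE = 25 × sqrt(1/100 + 1/160) = 3.19, and power is about 88%. The table is therefore an upper bound for variable-ratio matching.

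**Supply.** Full 1:2, 1:3 and 1:4 need 200/1,065 = 18.8%, 300/1,065 = 28.2% and 400/1,065 = 37.6% of the 2019 admissions to be usable. The documents do not give the usable fraction.

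**Sensitivity.**
- SD 15, 10 points: power is already 99.7% at 1:1. The half-width falls from 4.2 to 3.3 points at 1:4.
- 80 evaluable CGM patients, or a design effect of 1.25 (both assumptions): 71.6% at 1:1; 83.2%, 87.3% and 89.3% at 1:2, 1:3 and 1:4.
- Within-set correlation of 0.2 (assumption), with variance multiplied by (1 − 0.2): 88.5% at 1:1, 95.5% at 1:2, 97.9% at 1:4.
- RQ4 illustration with assumed rates of 20% in controls and 12% with CGM: half-width 10.1 points at 1:1, 8.4 at 1:2, 7.5 at 1:4; power 34%, 40% and 45%.

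**The case against.** The strongest reply is that nothing here is wrong. All three power figures reproduce, the design meets its 80% target, and one control per patient is a legitimate choice. That stands.

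A reader might infer that the study is underpowered. The documents do not support this. SD 25 is given as an upper value. In the site's own cohort of 19 COVID-19 patients (II), the SD of time in range was 23 on day 1 and 16 on days 2-7. By the same formula, 100 per group gives about 87% power at SD 23 and 99% at SD 16. Positive correlation within matched sets would add further margin.

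A reader might also infer that about ten ready controls exist per CGM patient. They may not. The 1,065 counts only the glucose criterion, before the participant exclusions, the six-factor matching and the requirement for at least three POC values a day. Patients qualifying by IV insulin alone, and other years, could add to the pool, but neither number is given.

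Nor are extra controls free. RQ4 needs billing data, and the Patient Participant Schedule of Activities lists daily clinical variables alongside glucose.

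Finally, more controls only narrow the interval around the same contrast. They do not reduce bias from historical controls, or from comparing percent of CGM time with percent of POC readings. All of this limits the size of the gain, but none of it supplies a reason to stop at 100.

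**Conclusion.** This is a worthwhile, low-cost improvement and not an error. With 100 CGM patients, SD 25 and a 10-point difference, power rises from about 81% to at most 90%, 93% and 95% at full 1:2, 1:3 and 1:4, and the interval half-width falls from 6.9 to as little as 5.5 points. Actual gains will be smaller where some patients find few matches. If the SD is nearer 15, the benefit is precision only. In RQ4, which is exploratory and carries no power claim, it is modestly narrower intervals for patient-level outcomes; binary outcomes remain imprecise under the illustrative rates, and costs of materials and implementation do not depend on the control count.

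The conclusion rests on two conditions that the documents leave open: enough admissions must survive the exclusions and matching, and CGM and control patients must be analysed in one model with a between-group term.

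**What to change.** - **III.B and III.C (RQ3, RQ4):** replace the fixed 100 historical controls with up to 3 or 4 per CGM patient. Match exactly on the factors already listed, after applying the participant exclusions where the EHR allows, and let the ratio vary with availability. Where only one match is found, that set is as now.
- **III.D:** fit one joint model of CGM and control patients with a group term. Choose in advance either a matched-set effect or a control weight of 1/k.
- **III.B:** count the usable pool, then restate power from the effective number of controls, 100/mean(1/k), for SD 25 and SD 15.

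The cost is revised wording, a larger EHR and billing extract, and more matching work. No further patient is enrolled. Historical-control bias and the mismatch between CGM time and POC percentages need their own remedies.
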